For time-to-event analyses, if strata are too small for fitting separate baseline hazard functions, strata may be added as a categorical covariate to models instead. Whenever possible, however, analyses should be stratified by disease severity (with separate baseline hazard functions).

For **binary outcomes**, probabilities will be compared between the investigational agent and its control group using Cochran-Mantel-Haenszel tests (CMH) or logistic regression. If the numbers are sufficiently large, CMH tests will be stratified according to the planned randomization strata (disease severity and site pharmacy), as described above under “stratification”. Odds ratios (OR) with 2-sided 95% confidence intervals (CI) will be estimated using logistic regression models.

For longitudinally measured binary outcomes, the treatment effect through follow-up will be estimated with 95% confidence intervals using generalized estimating equations (GEE) with a logit link function; the treatment effect is estimated via the interaction between the indicator for treatment group and the indicator for follow-up (versus baseline) visits. When there is more than one follow-up visit, “visit number” (day) may be included as categorical variable in the model, for variance reduction; alternatively, “time” may be included as a continuous variable.

**Ordered categorical outcomes (pulmonary and pulmonary+)** will be compared between treatment groups using proportional odds models, and the summary OR will be estimated with a 2-sided 95% CI. Additionally, to aid the interpretation, the ordinal outcome will be dichotomized according to cumulative probabilities of the ordered categories, comparing treatment groups for proportions of participants in category 1, in the “best 2 categories”, “best 3 categories”, etc.; these comparisons will be performed using logistic regression (or stratified CMH tests).

For interim analyses of the ordinal outcomes, if one or more recently enrolled participants have died (i.e., their outcome status is known) but their current administrative follow-up has not yet reached the time point at which the treatment groups are to be compared (e.g., day 5), analyses will be restricted to participants with administrative follow-up greater or equal to the target time point.

Models will be adjusted for the baseline categories of the pulmonary+ outcome and for study pharmacy, by including the corresponding indicator variables in the model.

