- If the number of observations is too small to adjust for both categorical covariates, preference will be given to the adjustment for the pulmonary+ category at baseline. Site pharmacy categories may be collapsed as described above under “stratification”.
- For the initial futility analysis (after 150 participants per arm have Day 5 data), the adjustment for the pulmonary+ categories and pharmacy will be additive.
- For key analyses, unadjusted OR estimates will also be provided as sensitivity analyses.

The validity of the proportional odds assumption will be assessed by testing for heterogeneity in the log ORs (for the treatment effect) across the dichotomized cumulative ordered categories in the corresponding logistic regression model (partial proportional odds model, test for “unequal slopes”).

- The primary sensitivity analysis testing the proportional odds assumption will compare the unadjusted proportional odds model for the treatment comparison (null model) versus a partial proportional odds model that allows for “unequal slopes” across the dichotomized cumulative categories (i.e., when testing the proportional odds assumption for the treatment comparison with respect to the pulmonary outcome on Day 5, the model will allow for heterogeneous ORs across the Day 5 pulmonary categories) as well as

across the stratification covariates (i.e., the baseline pulmonary+ categories and site pharmacy strata) (full partial proportional odds model).

**Continuous outcomes** will be compared between treatment groups using ANCOVA models for comparing means, if the ANCOVA model assumptions hold. If the distributions of the continuous outcomes are skewed, outcomes may be transformed, or compared between treatment groups using rank-based methods, such as the Wilcoxon test, or quantile (median) regression.

Comparisons between treatment groups for a continuous outcome will be adjusted for baseline values of the outcome, for the purpose of variance reduction, unless there are concerns over model stability with such an adjustment. For this purpose, the baseline value will be included as covariate in the model (e.g., ANCOVA, linear mixed models).

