## 10.2 Early Assessment of Futility

### 10.2.1 Interim Monitoring Guidelines for Early Assessment of Futility

Early in the trial, enrolment is restricted to participants in disease severity stratum 1. When Day 5 data for the first (approximately) 300 participants (150 per study arm) are available, the DSMB will review interim data and use pre-specified guidelines for early evidence of sufficient activity of the investigational agent that justifies continuing enrolment for the agent and expanding eligibility criteria to include participants in disease severity stratum 2 as well as stratum 1. Because the risk-benefit trade-off may be more complex than can be captured in pre-specified guidelines, decisions to terminate an agent for futility will include a broad assessment of the available data, and may be postponed until more data is available.

The early futility monitoring uses two co-primary outcomes, denoted by “pulmonary” and “pulmonary+”, assessed on Day 5. Both are ordered categorical outcomes with 7 categories, described in section 4.1 of the protocol and in [Appendix A](#) to this SAP. The pulmonary outcome considers largely respiratory-related disease, similar to the ordinal outcome in the ACTT-1 trial. The pulmonary+ outcome has the same categories for pulmonary complications (e.g., requirements for oxygen), and additionally includes extra-pulmonary outcomes such as thrombotic, myocardial, and cerebral complications of COVID-19.

Guidelines for the early futility assessment are as follows:

- a. If the investigational agent is superior to placebo (i.e.,  $p \leq 0.3$  for a one-sided test) in both the pulmonary+ and pulmonary intermediate ordinal outcomes, then enrolment for the agent will expand to complete the trial.
- b. If there is insufficient evidence for superiority versus control (i.e., one-sided  $p > 0.3$ ) in each of the two outcomes, then stop randomization.
- c. If there is evidence (1-sided  $p < 0.3$ ) for an association for one endpoint and not the other, then the agent may or may not advance depending on the risk/benefit profile emerging from the data at this early stage. If the effect estimate for both outcomes is on the side of benefit, the preference would be towards advancing the agent and expanding enrollment to include disease severity stratum 2.

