The DSMB will be asked to review whether the discordance is attributable to a positive or negative effect on extra-pulmonary organ dysfunction (the difference in the two ordinal scale categories, the conditions included in pulmonary+ but not in the pulmonary endpoint), and whether the same ordinal outcomes assessed on other days yield similar results, and weigh the risk/benefit profile. For example, if there is a significant positive effect on the pulmonary score and the lack of significant effect on the pulmonary+ score is driven by a lack of difference in the milder thrombotic symptoms in category 4 of the pulmonary+ scale (e.g. deep venous thrombosis) and there is no evidence of any raised risk of thrombosis overall, the agent will advance. Conversely, if the agent is superior to the control group with respect to the pulmonary outcome, but clearly inferior to the control group with respect to the pulmonary+ outcome or has a concerning safety profile, it will not advance.

Analyses of the primary efficacy endpoint, time to sustained recovery, will also be provided to the DSMB, as supporting information. These analyses are described in section [8.1](#).

If available, subgroup analyses by nAb status at study entry (nAb negative or positive) will also be provided.

### 10.2.2 Analyses of the Pulmonary and Pulmonary+ outcomes on Day 5

- Treatment groups will be compared by intention to treat.
- For each of the two ordinal outcomes, the number and percentage of participants in each of the categories on Day 5 will be tabulated, and the OR of the active versus control group will be estimated using a proportional odds model with indicators for the investigational agent group (active versus control) and for the categories of the ordinal pulmonary+ outcome at baseline (to adjust for baseline severity of illness). The model will be stratified by site pharmacy.

The summary tables will show the adjusted summary OR with 95% CI, estimated as described above, as primary analysis. In addition, the unadjusted summary OR with 95% CI will be shown as sensitivity analysis (estimated using a proportional odds model without adjustment for the pulmonary+ baseline category or site pharmacy). In the case that the adjusted OR differs substantially from the unadjusted OR, the reason for the deviation will be explored.

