## Assessment of model assumptions

- For the pulmonary and pulmonary+ outcomes at Day 5, the proportionality assumption of the odds ratio will be assessed (by including the interaction between the treatment group indicator and indicators for the Day 5 cumulative ordinal categories in the model, as well as the interactions between the treatment group indicator and the indicators for the strata by baseline pulmonary+ categories and site pharmacy; this corresponds to testing for separate slopes using a partial proportional odds model, see section 3 under “ordered categories”). If there is evidence for non-proportionality, the summary odds ratio in the proportional odds model will still be used to quantify the treatment effect, and the analyses of the dichotomized ordinal outcome categories will be used to help interpret the treatment effect.
- The sample size of 300 (150 per study arm) is sufficient to detect a summary OR of 1.60 for the comparison of the investigational agent versus control for each of the two ordinal outcomes with 95% power. The power of the tests depends on the hypothesized OR and the hypothesized distribution in the control group used for the sample size calculations. At the time of the early futility review, the deviation of the observed distribution from the hypothesized distribution in the control arm will be assessed, and the impact on the power of the trial will be estimated.

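### The primary proportional-odds check sets an unadjusted model against one that also frees covariate terms, so a rejection cannot be attributed to a non-proportional treatment effect

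*SAP*

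**What the plan says.** SAP section 3 (Analysis Principles, ordered categorical outcomes) first gives the aim of the check: "testing for heterogeneity in the log ORs (for the treatment effect) across the dichotomized cumulative ordered categories". It then specifies a primary sensitivity analysis that "will compare the unadjusted proportional odds model for the treatment comparison (null model") with a larger model. That model allows unequal slopes for treatment over the Day 5 categories and also "across the stratification covariates (i.e., the baseline pulmonary+ categories and site pharmacy strata) (full partial proportional odds model").

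Section 10.2.2 (Assessment of model assumptions) describes the same check and refers back to section 3, but gives the extra terms as treatment interactions: "as well as the interactions between the treatment group indicator and the indicators for the strata by baseline pulmonary+ categories and site pharmacy".

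The treatment comparison itself is adjusted. Section 3 says "Models will be adjusted for the baseline categories of the pulmonary+ outcome and for study pharmacy", and section 10.2.2 includes the baseline categories "to adjust for baseline severity of illness". If non-proportionality is found, section 10.2.2 keeps the summary odds ratio and uses the dichotomized analyses to help interpret it.

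**The concern.** For the check to answer its stated question, the two models should differ only in whether the treatment log odds ratio may vary over the cut-points. As written, the smaller model has no baseline or pharmacy terms and the larger one does. Any association of those covariates with Day 5 status then improves the fit of the larger model and raises the test statistic, even when the treatment effect is exactly proportional. Under the section 10.2.2 description, treatment-by-stratum heterogeneity enters the statistic too. The null model is also not the adjusted model on which the futility assessment rests.

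Baseline is likely to be prognostic. In disease severity stratum 1 the baseline categories are oxygen-requirement levels (section 10.2.2), and the same levels define Day 5 categories 2 to 4 (Appendix A).

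What is at stake is interpretation. The DSMB could be told that the futility outcome shows non-proportionality when it does not, or a real departure could be missed because it is spread over many degrees of freedom. The section 3 check also applies to the ordinal analyses on other days (section 8.3).

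**Working it through.** **Inputs from the SAP.** "Both are ordered categorical outcomes with 7 categories" (section 10.2.1), so there are 6 cut-points and 6 − 1 = 5 df for treatment non-proportionality. "The sample size of 300 (150 per study arm) is sufficient to detect a summary OR of 1.60" (section 10.2.2), with 95% power at one-sided 0.30 (section 1.4). In stratum 1 there are 3 baseline categories. The check is taken at 0.05 under the general significance rule in section 3; no separate level is given.

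**Assumed, because the documents do not give them.** Day 5 distribution 25/25/20/12/10/6/2%; baseline mix 27/38/35%; 7 pharmacy strata with no effect of their own; baseline odds ratio per category 1, 1.5, 2 or 3; a likelihood-ratio test of the whole difference between the models.

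**Step 1: the plan's own figure.** Whitehead's formula: N = 12(z₀.₇₀ + z₀.₉₅)² / [(ln 1.6)²(1 − Σp³)] = 12(0.524 + 1.645)² / [0.470²(1 − Σp³)] = 255.6 / (1 − Σp³). N = 300 corresponds to Σp³ of about 0.147. For Σp³ from 0.03 to 0.25, power at 300 runs from 96.3% to 93.5%. The stated 95% is reproduced. The SAP gives no operating figure for the proportional-odds check.

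**Step 2: false rejection by simulation.** About 1,000 trials per cell; N = 300; treatment odds ratio 1.6, exactly proportional given baseline.

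| Models compared | df | OR 1 | OR 1.5 | OR 2 | OR 3 |
|---|---|---|---|---|---|
| A. Unadjusted null vs treatment unequal slopes + baseline and pharmacy main effects | 5+2+6 = 13 | 4.3% | 47.7% | 95.3% | 100% |
| B. Unadjusted null vs treatment unequal slopes + treatment-by-stratum terms, no stratum main effects | 13 | 6.3% | 23.7% | 66.1% | 98.2% |
| E. Unadjusted null vs treatment and baseline unequal slopes, pharmacy omitted | 5+12 = 17 | 12.3% | 50.4% | 94.8% | 100% |
| D. Section 10.2.2 terms, stratum main effects in both models | 13 | 6.5% | 7.3% | 6.1% | 6.9% |
| C. Same covariates in both models, only treatment slopes freed | 5 | 6.0% | 7.1% | 6.1% | 4.5% |

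Monte Carlo error near 5% is √(0.05 × 0.95 / 1000) ≈ 0.7 points. With no treatment effect and baseline OR 2, the rates are A 96.2%, B 68.6%, E 95.6%, D 7.5% and C 6.8%.

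**Step 3: all covariates with unequal slopes.** This is the fullest reading of section 3: 5 + 6×2 + 6×6 = 53 df. The likelihood-ratio statistic for the baseline main effect (2 df) averaged 12, 27 and 62 for OR 1.5, 2 and 3, so its noncentrality is about 10, 25 and 60. Against the 53-df critical value of 71.0, a noncentral chi-square gives about 24%, 67% and 99%. This is asymptotic; cells would be sparse at N = 300.

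**Step 4: dilution of power.** A departure that the 5-df test detects with 80% power has noncentrality 12.8. If the added terms have no effect, the same departure is detected with 62% power at 13 df, 56% at 17 df and 32% at 53 df.

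**The case against.** The strongest defence is that section 3 already names the right target, heterogeneity of the treatment log odds ratio, straight after saying that the models are adjusted. Section 10.2.2 then writes the extra terms as treatment interactions, and the SAP's convention for interactions (section 9.1) is to add them to a model that already holds the main effects. If stratum main effects are in both models (row D), size is close to nominal whatever the prognostic strength of baseline. That much stands. But this reading contradicts the word unadjusted in section 3, and the test would still mix cut-point heterogeneity with treatment-by-stratum heterogeneity.

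Nor does the SAP name a joint likelihood-ratio test. A Wald test of the treatment-by-cut-point terms alone, in the larger model, would not be driven by baseline. That is fair, but section 3 describes a comparison of the two models, which is naturally read as a joint test.

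The unadjusted odds ratio is itself a planned sensitivity analysis, so an unadjusted null is not foreign to the plan. It is still not the model behind the primary futility result.

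A reader might infer that the futility decision is at risk. The documents do not support that: section 10.2.2 keeps the summary odds ratio whatever the check shows, the p≤0.3 guideline in section 10.2.1 does not use the check, and the dichotomized analyses are planned in any case, with a caution about multiplicity.

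**Conclusion.** The check is wrong as written, with consequences limited to interpretation. An unadjusted null set against a model that also frees baseline and pharmacy terms does not isolate the stated target. For the versions that include pharmacy (A, B and the 53-df version), false rejection at a nominal 5% is about 24-48%, 66-95% and 98-100% for baseline odds ratios of 1.5, 2 and 3 per category. These figures rest on the assumed prognostic strengths, Day 5 distribution, baseline mix, 7 pharmacy strata and a joint likelihood-ratio test. The direction follows from the model structure; the size does not.

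A reader might go further and conclude that the check rejects because of baseline rather than non-proportionality. That is too strong. A true departure can also cause rejection, and A and B are near nominal (4.3% and 6.3%) when baseline is not prognostic; version E is at 12.3% even then. What can be said is that a rejection cannot be attributed to the treatment effect, and that a non-rejection is weaker evidence than a 5-df test would give.

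**What to change.** In sections 3 and 10.2.2, define the check identically:

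- Both models contain the same additive baseline pulmonary+ and (collapsed) site pharmacy terms, with proportional slopes.
- The larger model differs only in freeing the treatment slope across cut-points: 5 df for 7 categories, fewer if categories are empty or merged.
- Name the test statistic.
- Report treatment-by-stratum heterogeneity as a separate test.

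In the simulation the matched check has size 4.5% to 7.1% across the assumed baseline strengths. The cost is SAP wording and analysis code; no new data are needed and the futility rule is unchanged.

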### Censoring for time-to-event analyses

For **interim** analyses, the type of censoring used will depend on the data collection schedule.

- If the reporting of the endpoint is data-driven (e.g., SAEs and deaths are reported as they occur), then follow-up is censored at the administrative censoring date, at the date of withdrawal, or loss to follow-up, whichever occurs earliest.
- If the date of the event is elicited retrospectively at fixed study visits spaced more than one week apart (e.g., “sustained recovery”), follow-up will be censored at the last day the endpoint status was ascertained.
- Sensitivity analyses will be provided for key analyses when the outcome status is uncertain.

For **final** analyses, follow-up will be censored on the last day the outcome status was ascertained.

**Adverse events** (AEs) will be classified by system organ class according to MedDRA® (currently version 24.1 [September 2021] is used; when new versions are implemented, items are recoded). AEs will be graded according to the *DAIDS Table for Grading the Severity of Adult and Pediatric Adverse Events, Corrected Version 2.1* (July 2017) (also referred to as the *DAIDS AE Grading Table*). Cause of death will also be coded according to MedDRA®.

The number and percent of participants with grade 1-4 AEs will be summarized by day and grade, and by MedDRA® System Organ Class and grade. The percentage of participants with AEs will be compared between treatment groups according to grade cut-offs, e.g., “percent of participants with any AE”, “percent of participants with grade 2 or higher AEs”, etc., using CMH tests. The total number of events and median (IQR) of events per participant will also be summarized.

Additionally, the incidence of grade 3 and higher AEs will be summarized (number and percent of participants), and compared between treatment groups using time-to-event methods.

**Significance level, two-sided tests:** Unless noted otherwise, statistical tests and confidence intervals will be 2-sided, confidence intervals will have approximate 95% coverage probability, and test results with P-values  $\leq 0.05$  will be considered “significant”. Percentages will be reported to at least one decimal place. P-values will be given to 2 significant figures.

**Cut-date for interim reviews:** Analysis data sets will be frozen (locked) several days (or weeks) prior to the review date, to allow the unblinded statisticians time to prepare a consistent

---

 The Medical Dictionary for Regulatory Activities terminology is the international medical terminology developed under the auspices of the International Conference on Harmonization of Technical Requirements for Registration of Pharmaceuticals for Human Use (ICH). MedDRA® is a registered trademark of the International Federation of Pharmaceutical Manufacturers and Associations (IFPMA)

report. The cut-date may be earlier than the date of the data freeze, to allow for lag time in the reporting of events. Early in the trial, the cut date and freeze date will be very close to the review date, to ensure timely safety reviews.

## 4 Enrolment and Eligibility

For the open report, the following enrolment and eligibility summaries will be provided:

- Enrolment over calendar time: plot by day or week, cumulative and increments.
- Enrolment by site pharmacy and by country: number (%)
- Eligibility: number (%) and reasons for eligibility violations

These summaries will be provided overall, and by disease severity randomization stratum.

For the closed report, enrolment and eligibility violations will be summarized by treatment group.

## 5 Baseline Characteristics

Baseline characteristics will be based on information collected on baseline and screening forms. For the open report, baseline characteristics will be summarized pooled across the two treatment groups (investigational agent and the “pooled” control group as described in section 2 above).

For the closed report, baseline characteristics will be summarized by treatment group.

The following baseline characteristics will be reported; unless noted otherwise, categorical variables will be summarized with numbers (%) in each category, and continuous variables will be summarized with median (IQR); in the open report, in addition, the mean (SD) and range may be provided. When enrolment has been completed, frequency distributions of these characteristics, including cut points for discretizing continuous measures, will be considered for defining subgroups in the final report.

- Demographics
  - Age: distribution in categories 18-29, 30-39, 40-49, 50-59, 60-69, 70-79,  $\geq 80$  years; and summary as continuous variable
  - Sex at birth: number (%) male, female
  - Ethnic group: number (%) Asian, Black, Latino/Hispanic, White, other
  - Type of residence (“home”)
  - Country of enrolment
- COVID-19 related characteristics
  - Duration of symptoms prior to enrolment
  - Use of remdesivir prior to enrolment
  - Pulmonary and pulmonary+ ordinal outcomes, number (%) in each category
  - NEWS: summary as continuous variable
  - Respiratory function scale (modified Borg dyspnea scale; continuous outcome)

- Disease severity randomization stratum (for investigational agents that enrol in both strata), number (%) in each category
- Receipt of SARS-CoV-2 vaccination, and type of vaccine (and if received as part of a blinded clinical trial, in which case the vaccine may be active or control)
- Other clinical characteristics
  - Concomitant treatments
  - Corticosteroid use will be summarized overall, and separately by oxygen requirement at baseline (no supplemental oxygen, < 4 L/min, conventional supplemental oxygen  $\geq$  4 L/min, high-flow oxygen or mechanical ventilation/ECMO)
  - History of chronic conditions (cardiovascular disease, diabetes, asthma, chronic obstructive pulmonary disease, hypertension, chronic kidney disease, hepatic impairment, cancer, or immunosuppressive disorder [HIV, and other than HIV])
  - Prior cerebrovascular event
  - Prior myocardial infarction (MI)
  - Requirement of continuous chronic supplemental oxygen
  - BMI (<30, 30-39.9, 40+)
  - Pregnancy (not applicable to protocol versions 2 and 3)
- Laboratory values: as continuous outcomes, and number (%) of grade 3 or 4 abnormalities according to the *DAIDS AE Grading Table*.

Some biomarkers will be measured centrally from stored samples, for example, hsCRP, IL-6, D-dimer, SARS-CoV-2 antibody, antigen, and viral RNA levels, and SARS-CoV-2 genome sequencing and variant identification. If these measures are available, they will be included in interim reports.

